6.1.3 Phase III: Time from initial FCM treatment to further FCM treatment

Time (weeks) from the initial FCM treatment to further FCM treatment received in Phase III will be calculated as the integer of $(\text{date of the further FCM treatment in Phase III} - \text{date of the initial FCM treatment}) / 7 + 1$. The time duration will be summarized via descriptive statistics including number of subjects, median, minimum (min) and maximum (max). Initial treatment is defined as Day 0 of Phase I for responders in Phase I and Day 0 of Phase II for responders in Phase II. At any time before week 46 subject could receive a single dose of unblinded FCM treatment (i.e. the further FCM treatment) if RLS symptom is worsened.

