Non-Responders who do not meet the laboratory criteria for additional dosing will be discontinued from the study and treated for RLS as deemed appropriate by the referring physician. Subjects who are Non-Responders at the end of Treatment Phase I and met the necessary laboratory criteria (ferritin <300 ng/mL and a TSAT <45%) will consented for enrollment in Treatment Phase II of the study. These subjects will receive the first of two unblinded doses of FCM (undiluted slow IV push 750 mg 100 mg/minute) on Day 0 of Phase II, which will occur within 7 days of the completing Treatment Phase I visit. The subjects will then receive the second dose of FCM (undiluted slow IV push 750 mg 100 mg/minute) on Day 7. All treated subjects will have blood samples taken for hematology, chemistries and iron indices on Day 14. Treatment efficacy (IRLSS score), medication review and adverse events assessment by phone will be done on Day 28. All subjects will return to the clinic on Day 42 for end of study assessments. Subjects completing Treatment Phase II will be re-evaluated on Day 42 and defined as either a Responder or Non-Responder, using the same criteria described above. Subjects deemed as treatment Non-Responders will be discontinued from the study after final assessments are complete.

Subjects who are evaluated on Day 42 (Week 6) as **Responders** from either Treatment Phase I or Treatment Phase II will continue through into the 46-Week, Long-Term Extension Phase III of the study, and be monitored and assessed by phone for RLS symptoms (IRLSS and Hopkins RLS-Sleep Quality Questionnaire [HRSQ]) and adverse events on (approximately every 9 weeks) Weeks 15, 25, 34, 43 and 52 (final follow-up visit). During Phase III subjects may receive additional unblinded treatments with FCM if at any time the subject reports worsening of RLS symptoms (an increase >4 points on the IRLSS compared to the last evaluation captured for that subject) and laboratory criteria are met (ferritin <300 ng/mL and a TSAT <45%). Subjects will receive a single FCM 750 mg undiluted slow IV push at 100 mg/minute. See section 6.6 for dosing and assessment outline. No additional treatment will be allowed after the Week 46. A final face-to-face study visit will occur on Week 52 (approximately 365 days since initial Day 0 Treatment). If a clinic visit is not possible, final evaluation will be completed by phone.

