1.2 STUDY ENDPOINTS

1.2.1 Primary Efficacy Endpoint(s)

Primary efficacy endpoint in **Treatment Phase I** is to determine the effectiveness of FCM in improving RLS severity associated with IDA. Effectiveness will be evaluated by:

- IRLSS score change from baseline to Day 42 with comparison between FCM vs. Placebo.
- CGI-I at Day 42.

Primary efficacy endpoint in **Treatment Phase II** is to determine the effectiveness of an additional unblinded single FCM treatment in improving RLS severity in non-responders from Treatment Phase I. Effectiveness will be evaluated by:

- IRLSS score change from baseline (For Phase II the “baseline” is established on Day 42 of Phase I) compared to Day 42 of Treatment Phase II
- CGI-I at Day 42 in Treatment Phase II.

Primary efficacy endpoint in **Long-Term Extension Phase III** is to evaluate the duration of effect of FCM as defined as the number of weeks from the initial treatment without need for further treatment. Initial treatment is defined as Day 0 of Phase I for Responders in Phase I and Day 0 of Phase II for Responders in Phase II.

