In **Treatment Phase III**, responders from either Treatment Phase I or Treatment Phase II will continue through into this 46-week long-term extension phase of the study, and be monitored and assessed by phone for RLS symptoms (IRLSS and HRSQ) and adverse events on Weeks 15, 25, 34, 43 and 52 (final follow-up visit) from treatment Phase I Day 0. During Phase III, subjects may receive additional unblinded treatments (i.e. a single FCM 750 mg undiluted slow IV push at 100 mg/minute) if at any time the subject reports worsening of RLS symptoms (an increase > 4 points on the IRLSS compared to the last evaluation captured for that subject) and laboratory criteria are met (ferritin < 300 ng/mL and a TSAT $< 45\%$). No additional treatment will be allowed after the Week 46. A final face-to-face study visit will occur on Week 52. If a clinic visit is not possible, final evaluation will be completed by phone.

The Schedule of Events for Phases I, II and III are presented as Table 1.1 and Table 1.2

Table 1.1 Schedule of Events Treatment Phase I and Treatment Phase II

STUDY VISIT PROCEDURES	SCREENING	Treatment Phase I and Treatment Phase II				
	-14	DAY 0	DAY 7+1	DAY 14+3	DAY 28+3 (PHONE CONTACT)	DAY 42+3
Informed Consent	X					X**
Eligibility	X	X				X
Medical History, including prior iron therapy	X	X				
RLS History	X	X				
D/C oral iron products	X					
Site contact IRT	X					
Physical exam	X					X
Vital Signs	X	X	X			X
Height and Weight without shoes	X					
CHDQ	X					
HTDI	X					
IRLSS	X	X			X	X
HRSQ		X				X
CGI-I						X
PGI-I						X
MOS Sleep Scale		X				X
Hematology	X	X	X	X		X
Iron Indices	X	X	X	X		X
Chemistry	X	X	X	X		X
Vitamin D		X	X	X		X
Erythropoietin		X				X
Trace Element		X				
Urine Pregnancy test	X					
Study Drug		X	X			
Brain MRI	X					X
Concomitant Meds	X	X	X		X	X
Adverse Events		X	X		X	X

** All Subject will be consented to participate in Treatment Phase II prior to any study procedures being completed

Table 1.2 Schedule of Events Long-Term Extension Phase III

STUDY VISIT PROCEDURES	Week 15 Phone Contact	Week 25 Phone Contact	Week 34 Phone Contact	Week 43 Phone Contact	Week 52 EOS
IRLSS	X	X	X	X	X
HRSQ	X	X	X	X	X
MOS / PGI-I					X
Concomitant Meds	X	X	X	X	X
Adverse Events	X	X	X	X	X
Physical Exam / VS	See protocol Section 6.6 for procedures for additional FCM dosing				
Iron Indices / Chemistries / Hematology					X
FCM Dosing					

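### The formula in SAP 6.1.3 adds a week after dividing by 7, so each re-dosed subject's time to further FCM is one above completed weeks and up to one week too long

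*SAP*

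**What the plan says.** SAP 1.2.1 defines the Phase III primary efficacy endpoint as the "duration of effect of FCM as defined as the number of weeks from the initial treatment without need for further treatment". The clock starts at "Day 0 of Phase I for responders in Phase I and Day 0 of Phase II for responders in Phase II" (SAP 6.1.3).

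SAP 6.1.3 then gives the calculation: "Time (weeks) from the initial FCM treatment to further FCM treatment received in Phase III will be calculated as the integer of" the difference between the two treatment dates, divided by 7, plus 1. It calls the result a time duration and summarises it by number of subjects, median, minimum and maximum. SAP section 6 specifies no formal testing in Phase III.

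The documents also fix a day-to-week scale. The Protocol Study Synopsis has "Subjects who are evaluated on Day 42 (Week 6) as" Responders, which equates Day 42 with Week 6. It places the Week 52 visit at "approximately 365 days since initial Day 0 Treatment". SAP 1.3.1 counts the Phase III visit weeks from Phase I Day 0.

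**The concern.** The formula and the endpoint definition do not measure the same thing. The definition asks how many weeks passed from the initial dose. The formula returns the number of completed weeks plus one. If the 1 was meant to count both end dates, it would have to be added to the days before dividing by 7; added afterwards, it is worth seven days.

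The number at stake is the Phase III primary result. Protocol 8.5 planned a Kaplan-Meier estimate, but SAP 6.1.3 lists only the count, median, minimum and maximum, so no second estimate in that section would reveal the offset. The error also runs in one direction only: it makes the interval before re-dosing look longer.

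**Working it through.** **Inputs**

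- d = days from initial to further FCM treatment (SAP 6.1.3).
- SAP value: int(d/7 + 1). This equals int(d/7) + 1 for every whole d, so it does not matter whether the 1 is read as inside or outside the integer operation.
- Documents' week scale: Day 42 = Week 6 (Protocol Study Synopsis).

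**Step 1. Does the formula reproduce the documents' own conversion?** No worked value of the formula is given, so the scale is the check.

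| d (days) | Documents' week | int(d/7) | SAP: int(d/7 + 1) |
|---|---|---|---|
| 42 | 6 | 6 | 7 |
| 105 | 15 | 15 | 16 |
| 175 | 25 | 25 | 26 |
| 301 | 43 | 43 | 44 |
| 364 or 365 | 52 | 52 | 53 |

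Only Day 42 and the approximate Day 365 are stated as days in the documents; the other rows take the visit week times 7. Plain elapsed weeks reproduce every row and the SAP formula reproduces none. Day 42 serves here only to fix the scale and is not offered as a re-dosing date.

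The SAP alone points the same way. SAP 1.3.1 gives Phase I as 42 days, Phase III as 46 weeks and the end at Week 52 from Phase I Day 0: 42/7 + 46 = 6 + 46 = 52.

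**Step 2. Size against completed weeks.** int(d/7 + 1) - int(d/7) = 1 for every d. A constant shift moves the median, minimum and maximum by the same amount, so each is exactly 1 too high on this scale. In relative terms: 1/15 = 6.7% at Day 105, 1/25 = 4.0% at Day 175 and 1/46 = 2.2% at Day 322.

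**Step 3. Size against exact elapsed time.** Let r be the remainder when d is divided by 7. Then

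int(d/7 + 1) - d/7 = 1 - r/7 = (7 - r)/7.

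For r = 0 to 6 this runs from 7/7 down to 1/7. If all remainders are equally likely, the mean is (7 + 6 + 5 + 4 + 3 + 2 + 1)/49 = 28/49 = 0.57 week. The excess is a full week only when d is a multiple of 7, and it is never zero or negative.

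**Step 4. Does another reading of the word integer help?** If it meant rounding to the nearest whole number, the excess over d/7 would run from 4/7 (r = 3) to 10/7 (r = 4). That is no better.

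**Step 5. Values near the re-dosing limit.** Taking Week 46 as Day 46 × 7 = 322 is an assumption, since no section converts it to a day.

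- Phase I responder, Day 322: SAP 47, elapsed 46.0.
- Phase I responder, Day 321: SAP 46, elapsed 321/7 = 45.86.
- Phase II responder dosed on study Day 322, with Phase II Day 0 at study Day 42: d = 280, SAP 41, elapsed 40.0.
- The same with Phase II Day 0 at study Day 49: d = 273, SAP 40, elapsed 39.0.

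**The case against.** The strongest defence is that the formula is openly stated and gives a legitimate quantity: the ordinal week in which the dose falls, with Days 0 to 6 as week 1. That is arithmetically true. But neither SAP 1.2.1 nor 6.1.3 defines an ordinal week; both describe a duration. The defence therefore supports relabelling as an alternative remedy and does not support the text as it stands.

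A second objection is size. Completed weeks themselves understate elapsed time, by 0 to 6/7 week (mean 21/49 = 0.43), so a full week is the least favourable comparison; against exact time the mean excess is 0.57 week. The Phase III analysis is descriptive, the study ended early (SAP section 9), and no decision threshold uses the number. All of this stands and limits the importance of the point.

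A third is that the overall Phase III duration is not shown to be overstated. SAP 6.1.3 can produce a value only for subjects with a further FCM date. Subjects never re-dosed contribute nothing, and leaving them out pulls the summary towards shorter durations, possibly by more than this error. This also stands, so the claim is confined to the values of re-dosed subjects.

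Two stronger readings are tempting and not supported:

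- *A dose at the last permitted time is reported as Week 47.* This needs a Phase I responder, the Day 322 assumption, and the SAP 1.3.1 wording that "No additional treatment will be allowed after the Week 46". SAP 6.1.3 instead places the further dose before that week; on that wording the last day is Day 321, which returns 46. Phase II responders restart the clock and, in the cases worked above, return 40 or 41.
- *Permitted late doses will look like protocol violations.* Nothing uses this variable to judge dosing compliance. SAP 3.2 has the clinical team identify deviations.

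**Conclusion.** The calculation rule in SAP 6.1.3 is wrong for the endpoint it serves. Each re-dosed subject's value is exactly 1 above completed weeks and 1/7 to 1 week above exact elapsed time. The mean of 0.57 assumes that the remainders on division by 7 are evenly spread. The median, minimum and maximum are each 1 above their completed-week values, about 7% at Day 105 and about 2% near Week 46. The direction is always towards a longer apparent effect among those re-dosed.

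The conclusion rests on reading the endpoint as a duration, as SAP 1.2.1 words it, and on the documents' scale of Day 42 as Week 6. It does not depend on how the Week 46 limit is read. The consequence is modest, but the error is certain and sits in a primary endpoint, so it should be corrected.

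**What to change.** In SAP 6.1.3, replace the formula with (date of further FCM treatment - date of initial FCM treatment)/7, reported to one decimal, without truncation and without the added 1. Day 105 then gives 15.0 and Day 108 gives 108/7 = 15.4, where the present rule gives 16 for both. If the ordinal week of re-dosing is what is wanted, keep the formula, name the variable accordingly, and do not present it as duration of effect.

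The cost is one line of SAP text and one line of code, with no new data. The reported durations become slightly shorter.

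The correction will not put Phase II responders on the study-week scale, because their clock starts at Phase II Day 0 while visit weeks run from Phase I Day 0. A table footnote saying so would prevent misreading.

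Separately, the limit on further dosing is worded as before week 46 in SAP 6.1.3 and as not after Week 46 in SAP 1.3.1, the Protocol Study Synopsis, and Protocol 3.2 and 6.6. These passages must be reconciled.

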- 20. Any other pre-existing laboratory abnormality, medical condition, or disease that, in the opinion of Investigator, may cause the subject to be unsuitable for the study or place the subject at potential risk from being in the study, e.g. a malignancy, uncontrolled hypertension, unstable ischemic heart disease, or uncontrolled diabetes mellitus.
- 21. Subject is unwilling or has conditions that would prohibit them from complying with the study requirements.

RLS Therapy:

Subject should not be receiving treatment for RLS. All treatment for RLS should be discontinued at least 4 weeks prior to screening.

Study Duration – One year:

- Screening Phase: up to 14 days
- Treatment Phase I: 42 days
- Treatment Phase II: 42 days
- Long-term Extension Phase III: up to 46 weeks

Number of Subjects / Sample Size:

Enrollment is planned for completion (reaching Day 42 final assessment) of 70 randomized subjects (35 per treatment group). Based on Study 1VIT05009 in RLS subjects without IDA, approximately 50% of subjects in the FCM group and 15% of subjects in the placebo group are anticipated to have much or very much improvement on the CGI-I.³⁵ The proposed sample size provides >85% power to detect this difference with the chi-square test. The mean treatment difference and standard deviation of 5.0 (7.3) is estimated for change from Baseline to Day 42 for IRLSS score. The proposed sample size provides >80% power to detect this difference with the unpaired t-test.

Statistical Analyses:

The percentage responding to treatment will be evaluated for each drug condition in Treatment Phase I to determine the treatment difference at Day 42. This will be calculated from the IRLSS as change from Baseline and for the CGI-I with response determined as much or very much improved (scores of 1 or 2). All scores greater than 2 on the CGI-I are considered to indicate no significant response. For Phase II, the proportion of treatment non-responders in Phase I who respond to FCM in Phase II will be estimated and the IRLSS score, CGI-I, and PGI-I will be summarized at Day 42. The duration of treatment over the follow-up to end of study will be described as the percentage of responders and the IRLSS score change from Baseline at each time point. Time to first FCM dose after start of Phase III will be estimated with Kaplan-Meier methodology.

CONTACT PERSON FOR THE STUDY

For study related questions please contact:

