8.5 Statistical Analyses of Efficacy

Categorical variables will be summarized with the number and percent of subjects in each treatment group with the characteristic. Quantitative variables will be summarized with the mean, median, standard deviation, minimum value, and maximum value. Baseline will be defined as the last value obtained before randomization.

Phase I

The treatment differences for the changing IRLSS score from Baseline to Day 42 will be assessed with the analysis of covariance with treatment as a fixed effect and baseline value as a covariate.

The treatment difference for the percentage of subjects who are much or very much improved at Day 42 as measured by the CGI-I will be assessed with the chi-square test.

Change from Baseline for IRLSS at Day 28, MOS at Day 42, and brain iron distribution at Day 42 will be assessed with the same method as IRLSS at Day 42. The percentage of subjects who are much or very much improved at Day 42 as measured by the PGI-I will be assessed with the chi-square test.

Phase II and III

All analyses will be descriptive.

For Phase II, the proportion of treatment **Non-Responders** in Phase I who respond to FCM in Phase II will be estimated and the IRLSS, CGI-I, PGI-I and brain iron distribution will be summarized at Day 42.

The Kaplan-Meier method will be used to estimate time from first dose of FCM to treatment intervention. Subjects in Phase III who discontinue the study before requiring treatment intervention will be censored on the day of the last contact with the Investigator.

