2.4 HANDLING OF MISSING DATA

Missing data will not be imputed for descriptive statistical summaries in safety or efficacy analyses.

For the PGI-I score, missing data at Day 42 will be considered as failure in analysis.

Dates missing the day or both day and month of the year will adhere to the following conventions to classify TEAE and to classify prior/concomitant medications.

- A medication with a completely missing start date will be considered a prior medication. A medication with a completely missing stop date will be considered a concomitant medication.
- If complete AE onset date is missing and AE end date is on or after the first dose date then it will be counted as a treatment emergent AE (TEAE) for the study. If complete AE onset date is missing and AE end date is before the first dose date then it will be counted as a not treatment emergent AE (TEAE) for the study.
- If an AE or a medication has a partial missing start or stop date, the following rules will be used for imputation:
 - If year is present but month and day are missing, impute start date as January 1 of that year or first dose date if the year is the same as the year of first dose date and impute stop date as December 31 of that year.
 - If year and day are present but month is missing, impute start month as January or the month of the first dose date if the year and day is the same as the year and day of first dose date and impute stop month as December.
 - If year and month are present but day is missing, impute start date as first day of that month or first dose date if the year and month are the same as the year and month of first dose date and impute stop date as last day of that month.

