3. STUDY SUBJECTS

3.1 DISPOSITION OF SUBJECTS

Disposition will be summarized for all randomized subjects.

The disposition will include the following:

- Subjects who are randomized (for Phase I only)
- Subjects who are in Safety Population
- Subjects who are in ITT population
- Subjects who complete the study
- Subjects who discontinue the study

The number and percent of subjects will be summarized for each reason for premature discontinuation.

A listing of dispositions will be provided for all subjects.

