5. STUDY DRUG AND EXPOSURE

5.1 TREATMENT COMPLIANCE AND EXTENT OF EXPOSURE

Treatment compliance will not be summarized, as each subject will be treated in an inpatient setting to receive a single dose of study drug on Day 0 and Day 7 of Phase I or II or a single dose during any time before week 46 of Phase III.

The number (percentage) of subjects who received IV injections of study drug will be summarized by treatment phase, treatment group (for Phase I only) and overall for safety population. The number (percentage) of subjects who received additional IV injection of study drug in Phase III will be summarized for Phase III safety population.

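### The Phase III primary endpoint, duration of FCM effect, is summarised only in re-treated subjects, so the reported duration is biased short

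*SAP*

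**What the plan says.** SAP 1.2.1 defines the Phase III primary endpoint as "the number of weeks from the initial treatment without need for further treatment". The clock starts at Day 0 of Phase I for Phase I responders and Day 0 of Phase II for Phase II responders.

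SAP 6.1.3 derives it as the date of the further FCM dose in Phase III minus the date of initial treatment, divided by 7, plus 1, taken as an integer. It continues: "The time duration will be summarized via descriptive statistics including number of subjects, median, minimum (min) and maximum (max". It states no censoring rule. SAP 2.4 adds: "Missing data will not be imputed for descriptive statistical summaries in safety or efficacy analyses".

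The supplied protocol planned something else. Section 8.5 says: "The Kaplan-Meier method will be used to estimate time from first dose of FCM to treatment intervention", with subjects who discontinue before re-treatment censored at last contact. The same subsection opens with "All analyses will be descriptive". The synopsis agrees on the method: "Time to first FCM dose after start of Phase III will be estimated with Kaplan-Meier methodology".

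SAP 6 limits all phases to descriptive statistics. SAP 9 item 1 gives early termination as the reason for running no statistical analysis. SAP 9 does not list the loss of Kaplan-Meier and censoring for this endpoint.

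**The concern.** The endpoint is time free of re-treatment, but only subjects who were re-treated can contribute a value. Those who stay free of re-treatment, the best outcome on this endpoint, are left out. The SAP does not state this exclusion in words. It follows from a formula that needs a re-treatment date, with nothing to stand in for one.

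The more subjects remain free of re-treatment, or the earlier follow-up stops, the further the median falls below the true duration. No test depends on it. It is, however, the only planned estimate of duration in weeks for the Phase III primary objective, and a reader would take it as how long FCM lasts.

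**Working it through.** **Inputs from the documents.** Phase I responders enter Phase III at Week 6 (protocol 3.2). No re-treatment is allowed after Week 46, and weeks count from Phase I Day 0 (SAP 1.3.1). There are 35 subjects per arm, with 50% of the FCM arm expected to improve on the CGI-I (SAP 1.3.3). The documents state no duration or re-treatment rate, so there is no plan figure to reproduce.

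**Direction, in any data set.** With d re-treated subjects, the re-treated-only curve drops by 1/d at each event. Kaplan-Meier steps never shrink over time and sum to at most 1, so after k events they total at most k/d. The Kaplan-Meier curve therefore never lies below the re-treated-only curve.

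An invented example: 30 entrants, 10 re-treated at Weeks 10, 14, ..., 46, and 20 never re-treated. The re-treated-only median is 28 weeks (before the added week). Kaplan-Meier gives 20/30 = 67% event-free at Week 46, with the median not reached.

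**Size, under an assumed model.** Take a constant hazard λ from Week 6 and a share p re-treated by Week 46, which is 40 weeks later:

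- λ = −ln(1 − p)/40
- true median = 6 + ln 2/λ
- re-treated-only median = 6 − ln(1 − p/2)/λ

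If follow-up stops at Week 25, the share re-treated is q = 1 − exp(−19λ), and q replaces p in the last formula with λ unchanged.

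| p | True median (wk) | Re-treated-only, to Week 46 | Too low by | As the SAP would print it | q at Week 25 | Re-treated-only, to Week 25 | Too low by |
|---|---|---|---|---|---|---|---|
| 94% | 15.9 | 15.0 | 5% | 16 | 74% | 12.5 | 21% |
| 75% | 26.0 | 19.6 | 25% | 20 | 48% | 14.0 | 46% |
| 50% | 46.0 | 22.6 | 51% | 23 | 28% | 14.7 | 68% |

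**The added week.** The formula reports 70 days as 70/7 + 1 = 11 weeks. For intervals of 42 to 322 days it exceeds days/7 by 0.14 to 1.0 week, 0.57 on average. An excess of 0.5 to 1.0 week offsets the bias fully only if no more than about 4% to 7% of subjects remain un-re-treated at Week 46.

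**What Kaplan-Meier would recover.** I simulated 4,000 trials of 18 entrants (35 × 50% = 17.5, rounded up), with follow-up cut off uniformly over Weeks 15 to 46.

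- p = 75%: the Kaplan-Meier median is reached in about 90% of runs and is typically about 25 weeks (true 26.0). The re-treated-only median is about 15.
- p = 50%: the Kaplan-Meier median is reached in about 40% of runs and, when reached, is about 33 weeks (true 46.0). The re-treated-only median is about 17. The Week 25 event-free proportion averages 72% (true 72%), with SD 11 points.

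**Window for Phase II responders.** Phase II Day 0 falls within 7 days of Day 42, nominally on study days 42 to 49, and Week 46 is day 322. Their own clock can reach at most (322 − 42)/7 = 40 or (322 − 49)/7 = 39 weeks.

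**The case against.** **Durability is described elsewhere.** SAP 5.1 says: "The number (percentage) of subjects who received additional IV injection of study drug in Phase III will be summarized for Phase III safety population". SAP 3.1 says: "The number and percent of subjects will be summarized for each reason for premature discontinuation". SAP 6.2.10 gives IRLSS change at Weeks 15 to 52, and SAP 9 item 3 reports completers. This stands in part: a reader can see how many subjects the median leaves out. None of these is a duration, and none corrects the median.

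**The protocol in force may differ.** The SAP cites a version dated 4 September 2019; the supplied one carries April 2016 dates. A later change of method cannot be ruled out, and SAP 9 item 1 could be read to cover Kaplan-Meier. That limits the charge of an unexplained departure. It does not affect the bias, which lies in SAP 6.1.3 itself. The supplied protocol also treats Kaplan-Meier as descriptive, so dropping tests does not require dropping it.

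**Not re-treated is not the same as still benefiting.** Under protocol 4.5, subjects who worsen but fail the laboratory criteria, or who want another RLS treatment, can leave without further FCM. Censoring them could overstate duration. This stands, and the fix needs a sensitivity analysis for it.

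**The sizes are illustrative, and Kaplan-Meier has limits with few subjects.** The hazard, re-treatment shares and cut-off pattern are assumed. The 18 entrants omit placebo responders, Phase II responders and those who qualify through an IRLSS of 10 or less. At 50% re-treated, the Kaplan-Meier median is itself low when it is reached. This stands, and is why event-free proportions should lead. At 94% the printed figure would happen to be right, but only because two errors cancel.

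**Conclusion.** The concern holds: SAP 6.1.3 is wrong as written and should be fixed. Before rounding, leaving out un-re-treated subjects can only shorten the apparent duration. The size rests on assumptions (constant hazard from Week 6, assumed re-treatment shares): 5%, 25% or 51% too low when 94%, 75% or 50% are re-treated by Week 46, and 21%, 46% or 68% if follow-up stops at Week 25. The added week cancels the error only when almost everyone is re-treated. The study did terminate early, which pushes towards the larger figures. No hypothesis test is affected; what is misstated is the descriptive answer to the Phase III primary objective.

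**What to change.** In SAP 6.1.3, restore a descriptive Kaplan-Meier analysis of all Phase III entrants:

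- Report numbers at risk, events and censored, the event-free proportion at scheduled weeks with 95% CI, and the median only if reached.
- Keep further FCM as the main event. Censor subjects without an event at the earlier of last contact and the end of the re-treatment window (study Week 46, about Week 39 to 40 on a Phase II responder's clock). Give no estimate beyond it.
- Show Phase I placebo responders separately, because their Day 0 dose was saline.
- Add a sensitivity analysis that also counts withdrawal for worsening RLS or for alternative RLS treatment as an event.
- Report time as days/7 without the added week.
- Keep the re-treated-only summary as supplementary, labelled as such, and record in SAP 9 any remaining departure from the protocol in force.

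The cost is SAP wording and one descriptive table. It needs dose dates, last-contact dates and discontinuation reasons. The CRF was not supplied, but protocol 8.5 and SAP 3.1 and 6.1.3 already depend on these items. With few subjects the intervals will be wide and the median may not be reached.
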